Relatedly, we examined the effectiveness of two postpartum smoking relapse preventions as a function of prenatal depressive symptoms ([name] et al., 2020). People with clinically significant depressive symptoms late in pregnancy did not maintain smoking abstinence in the postpartum if they received a standard intervention with behavioral techniques to manage cigarette cravings (SUPPORT). However, as seen in Figure 3, those who were depressed late in pregnancy were more successful maintaining abstinence if they received a smoking abstinence intervention that was tailored to psychosocial factors such as mood (STARTS). These results highlight the importance of depressive symptomatology in postpartum tobacco abstinence and the significance of addressing prenatal depressive symptoms for long-term impact on maternal and child health. Thus, we propose to

invite people who use tobacco and cannabis and experienced elevated depressive symptoms during pregnancy to partner with us in an intervention development project to reduce tobacco-related health inequities.

Study Design

1. Total number of subjects to be enrolled at this site (enter -1 for chart reviews, banking, registries):

25

2. Describe and explain the study design:

This study is an experimental, single-arm feasibility trial.

3. Describe the primary and secondary study endpoints:

The primary outcomes of the trial is the feasibility and acceptability of the novel intervention and abstinence from tobacco and cannabis use. Feasibility and acceptability of the intervention will be assessed using attendance, completion of intervention-related procedures, and the Acceptability of Intervention Measure (AIM). Abstinence will be measured by proportion of the participants who self-report no use of either substance and by calculating the proportion of participants with negative urine screens for THC and COT. Secondary outcomes include changes in depressive symptoms, tobacco, and cannabis use from the baseline assessment in pregnancy to 3 months postpartum.

4. Provide a description of the following study timelines:

Duration of an individual subject's active participation:

Depending on gestation age at enrollment, subjects will actively participate in the study for approximately 6 to 12 months.

Duration anticipated to enroll all subjects:

9/30/2026

Estimated date for the investigator to complete this study (complete primary analyses):

10/1/2027

5. List the inclusion criteria:

- (1) <26 weeks of gestation

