- (2) English speaking
- (3) confirmed pregnant
- (4) plan to remain pregnant
- (5) use of combustible tobacco at least once a week during pregnancy, or at least once a week in the 3 months before pregnancy if stopped
- (6) use of cannabis at any frequency during pregnancy or in the 3 months before pregnancy if stopped

English speaking is a requirement since study materials are in English and intervention sessions will be conducted in English.

6. List the exclusion criteria:

- (1) current opioid use or active treatment for Opioid Use Disorder
- (2) unable to provide informed consent in English
- (3) under 18 years old

7. Will children or any gender, racial or ethnic subgroups be explicitly excluded from participation?

☒ Yes ☐ No

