5: Mindfulness skills. This may include teaching of nonjudgmental emotional awareness, nonjudgmental awareness of management of urges, and trauma-informed adaptations to mindfulness practice.

End of Intervention Assessment (T2):

This assessment will occur when participants are 32-36 weeks gestation. Participants will complete the following questionnaires on REDCap as part of the end-of-intervention assessment: Demographics, EPDS, Smoking and Alcohol Use Questionnaire, Cannabis Use Questionnaire, Perceived Stress Scale-4, and Everyday Discrimination Scale. Participants will be paid \$50 using the Pitt Vincent payment system when questionnaires are completed.

1-month Postpartum Assessment (T3):

Participants will complete the following questionnaires on REDCap as part of the 1-month postpartum assessment: Demographics, EPDS, Smoking and Alcohol Use Questionnaire, Cannabis Use Questionnaire, Perceived Stress Scale -4, and Everyday Discrimination Scale. Participants will be paid \$70 using the Pitt Vincent payment system when questionnaires are completed.

3-month Postpartum Assessment (T4):

This assessment will be scheduled to occur in person at Bellefield Towers or at an agreed upon location convenient to the participant. Participants will complete the following questionnaires and interviews: Demographics, EPDS, Smoking and Alcohol Use Questionnaire, Cannabis Use Questionnaire, Perceived Stress Scale-4, Everyday Discrimination Scale, Acceptability of Intervention (AIM), Additional Treatments, Timeline Follow-back and OB/Neonatal outcomes. Following completion of the questionnaires and interviews, participants will be paid \$100 using the Pitt Vincent payment system. Participants will be asked to provide a urine sample as contingency management, which will be tested for the presence of cotinine (COT) and THC. Participants will receive an additional \$50 if their sample tests negative for both substances.

Urine collection:

Participant will be provided with a sterile urine collection cup and directed to a nearby bathroom where they can collect their sample independently. Participants will be offered an opaque bag to transport urine sample cup back to the assessment location. Research staff will follow testing procedures for the THC and COT dip tests and then dispose of all testing and collection equipment in a hazardous waste bin or bag.

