De-identified data from the project will be saved in a database prepared for the study. The database will be password protected. The MPIs will make deidentified data collected from research participants available to other researchers and community partners after the study is completed and the final report has been generated. Data will be provided in the form of Excel files containing only ID codes as subject identifiers. No identifying information, including names, telephone numbers, or addresses, will be made available. Researchers requesting use of data must submit their request in writing to the MPIs, including the purpose for which they are requesting use of the data. These requests will be reviewed by the Investigators and will require engaging in a Data Use Agreement (DUA), in cooperation with the University of Pittsburgh. Data will be of sufficient quality to allow other investigators to validate and replicate research findings, consistent with NOT-OD-21-013. Updates on data sharing activities will be provided in annual progress reports to the funding organization.

- 3. If any research data is collected, stored, or shared in a paper format, address what precautions will be used to maintain the confidentiality of the data:**

Paper documents are kept in locked filing cabinets in an office of the Western Psychiatric Hospital at the University of Pittsburgh. Access to subject data records will be given only to the PI and study staff supervised by Drs [name] and [name].

Specimens and Related Data

1. * Data and Specimens will be stored:

Limited time (i.e., only until the study is completed)

2. * Indicate the type of specimen, describe where stored, and for how long:

Participants will be asked to provide one urine sample during their final assessment.

The sample will be tested for cotinine and THC and then disposed of immediately after this testing.

3. * How the specimens will be accessed and who will have access to the specimens:

The urine sample will be collected by the participant and accessed only by the research staff testing the sample.

4. * List the data to be stored or associated with each specimen:

The results of the THC and cotinine dip tests, date and time of the test, participant ID number, and documentation of payment for negative results will be recorded in a secure study database.

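### The urine measure of abstinence is one unconfirmed dip at T4, not tied to self-report or baseline, so it can count unchanged light users as abstinent

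*Protocol*

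**What the plan says.** Study Aims item 1 and Study Design item 3 list abstinence among the primary outcomes and give it two measures. The first is self-report: "Abstinence will be measured by proportion of the participants who self-report no use of either substance". The second is urine: "calculating the proportion of participants with negative urine screens for THC and COT". Neither section says how the two combine or which prevails when they disagree.

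Study Design item 5 sets the entry floor. For tobacco it is "use of combustible tobacco at least once a week during pregnancy", or the same frequency in the 3 months before pregnancy for those who have stopped. For cannabis it is "use of cannabis at any frequency during pregnancy or in the 3 months before pregnancy if stopped".

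On collection, Specimens and Related Data item 2 states: "Participants will be asked to provide one urine sample during their final assessment". Under Research Activities, the T1 assessment consists of questionnaires only. For the T4 sample, "Research staff will follow testing procedures for the THC and COT dip tests and then dispose of all testing and collection equipment". No laboratory confirmation, cut-off or detection window is given. The T4 visit is scheduled with the participant, and a sample negative for both substances earns $50.

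The T4 battery also includes "Additional Treatments, Timeline Follow-back and OB/Neonatal outcomes", but the protocol does not say what the Timeline Follow-back feeds. Study Design item 8 treats the dip result as biochemical verification of abstinence and places it under secondary analysis, whereas item 3 lists it under the primary outcome.

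**The concern.** This point is about participants who are still using at T1. A negative dip shows only that nothing was detected over whatever period the test covers. In a daily user it is reasonable evidence of a change. In someone who smokes once a week and uses cannabis once a month, it may simply mean that the sample fell between two occasions of use. The urine rule has nothing to separate the two cases: no T1 sample, no minimum abstinent period and no agreement with what the participant reports. A short pause timed to the scheduled, rewarded visit would also satisfy it.

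The design is single-arm, so no concurrent group shows how often a negative dip occurs when use has not changed. This error can only raise the urine proportion, and some part of an observed rate could be read as preliminary efficacy when nothing has changed. Because the specimen is discarded after testing, it cannot be retested later.

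**Working it through.** The protocol states no misclassification rate, detection window or expected mix of users, so there is no figure to reproduce. The check asks what urine-negative proportion would be seen if nobody changed their use.

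**Inputs from the protocol.** Tobacco at least weekly; cannabis at any frequency; one sample at T4; negative required on both tests; 25 participants.

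**Assumptions (not in the protocol).**
- Detection window *w* of 2, 3, 4 or 7 days, the same for both tests.
- Light users make up 10%, 20% or 40% of those enrolled.
- Light users fall equally into four profiles: tobacco 1 or 2 times a week, crossed with cannabis once in 30 days or once a week.
- Everyone else always tests positive.
- Tobacco and cannabis occasions are independent, and so is the sampling time.

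**Formulas.** With use every *k* days on average:
- Poisson (random) use: P(negative) = exp(−*w*/*k*).
- Evenly spaced use: P(negative) = max(0, 1 − *w*/*k*).
- Both tests negative: the product of the two.

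**One profile worked through** (tobacco weekly, cannabis monthly, *w* = 2):
- Poisson: exp(−2 × (1/7 + 1/30)) = exp(−0.352) = 70%.
- Evenly spaced: (1 − 2/7) × (1 − 2/30) = 0.714 × 0.933 = 67%.
- At *w* = 7 the same profile gives 29% under Poisson use and 0% under evenly spaced use.

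**Average over the four profiles.** For Poisson use at *w* = 2, (70.3 + 56.5 + 52.8 + 42.4)/4 = 55.5%. The other cells follow in the same way.

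| Window (days) | Poisson | Evenly spaced |
|---|---|---|
| 2 | 55.5% | 47.1% |
| 3 | 41.9% | 26.3% |
| 4 | 31.8% | 13.9% |
| 7 | 14.6% | 0% |

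**Urine-negative rate with no change in use** = light-user share × average above, in percentage points (Poisson / evenly spaced):

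| Window (days) | 10% light | 20% light | 40% light |
|---|---|---|---|
| 2 | 5.6 / 4.7 | 11.1 / 9.4 | 22.2 / 18.8 |
| 3 | 4.2 / 2.6 | 8.4 / 5.3 | 16.7 / 10.5 |
| 4 | 3.2 / 1.4 | 6.4 / 2.8 | 12.7 / 5.6 |
| 7 | 1.5 / 0 | 2.9 / 0 | 5.8 / 0 |

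In a sample of 25 each participant is 4 points, so the range runs from none to between five and six participants (0.222 × 25 = 5.6).

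**With a truthfully reported 28-day abstinent period added.** Under Poisson use the profile average is mean exp(−28 × rate) = 0.19%, which gives 0.02, 0.04 and 0.08 points for 10%, 20% and 40% light users. Under evenly spaced use it is 0.

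**The case against.** Four objections carry weight.

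1. **Size.** A reader might infer that light users will often be counted as abstinent, or that the no-change rate will usually exceed 5 points and rival the 10% control quit rate in Study Design item 8. The documents do not support either inference. Both need a detection window and a light-user share that the protocol does not give. Random use also fits the entry wording poorly: a Poisson rate of one a week leaves exp(−1) = 37% of weeks with no use. Evenly spaced use gives smaller figures, falling to 0 at 7 days. The 10% belongs to a two-arm comparison led by self-report, so it is not a benchmark for this measure. This objection stands.

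2. **Scope.** A reader might infer that the whole abstinence outcome is compromised. It is not. Self-reported abstinence is a separate co-listed measure, and item 8 leads its efficacy analysis with it. Change in use from baseline is a secondary outcome. A truthful weekly smoker would appear as a user on the T4 questionnaires and the Timeline Follow-back. This also stands: the error is confined to the urine proportion.

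3. **Detail for the SAP.** Look-back periods and derivations are commonly left to a SAP, and item 8's label could be read as self-report checked by urine. This does not dispose of the point. The protocol fixes the urine measure in two sections as the proportion with a negative screen, and item 8 describes the verification as the dip itself. A SAP requiring agreement with self-report would be changing that stated rule.

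4. **Consequence.** The hypotheses concern feasibility and acceptability, and no abstinence threshold or progression rule depends on the dip. That limits the consequence, but the measure is still listed under the primary outcome.

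**Conclusion.** The point holds in a limited form. As written, the urine measure can count participants with unchanged light use, or a brief pause before the visit, as abstinent. That follows from the entry floor, the single unconfirmed T4 dip, the lack of a baseline sample and the lack of any link to self-report, and it needs no outside figure.

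Its size cannot be judged from the documents. Under the stated assumptions the no-change urine-negative rate lies between 0 and about 22 points. Evenly spaced use and long windows are at the low end; Poisson use, short windows and many light users are at the high end. If the two substances tend to be used on the same occasions, the double-negative chance would be higher than the independence product used here.

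Participants who had already stopped before T1 can also be urine-negative at T4 without any change. They are outside the calculation, but they are a further reason to show the result by T1 status. The change is worth making because it replaces a stated rule with a less biased one at little cost.

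**What to change.** In Study Aims item 1 and Study Design items 3 and 8, define verified abstinence at T4 as no tobacco and no cannabis use on the T4 Timeline Follow-back over a fixed, pre-stated look-back, together with a dip negative for both substances. A look-back of 28 days is one example. The protocol does not give the follow-back's recall length, so it must be set to cover the chosen period. The dip can then overturn a self-report but cannot establish abstinence by itself.

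Keep the raw negative-dip proportion as a descriptive figure only, tabulated by T1 use frequency and status (still using or already stopped) from the T1 questionnaires. State the same order of measures in items 3 and 8, so that the urine result is not primary in one and secondary in the other.

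The cost is endpoint wording and one derived variable, with no new visit, sample or staff. The reported rate will be somewhat lower and will depend partly on recall. The residual no-change rate is near zero only if recall is truthful; where it is not, the dip catches only use recent enough to be detected.

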In addition to the incentive for completing assessments, we have budgeted up to \$50 for a clean (i.e., no evidence of tobacco and cannabis use) sample as a contingency management incentive at the final postpartum assessment (T4).

Participants will be paid using Vincent, the University's approved payment system. There will be no compensation for partial completion of T1, T2, or T3. At T4, participants will be paid separately for completing all questionnaires (\$75) and interviews (\$25).

5. Recruitment materials: (attach all material to be seen or heard by subjects, including advertisements and scripts)

	Document	Category	Date Modified	Document History
View	Recruitment Scripts(1)	Recruitment Materials	2/3/2026	History
View	Intervention Screening Survey(2)	Recruitment Materials	1/30/2026	History
View	Recruitment flyer(1)	Recruitment Materials	1/6/2026	History

Study Aims

1. * Describe the purpose, specific aims, or objectives and state the hypotheses to be tested:

Guided by the PICTURe community collaborative, we will conduct a single group, proof-of-concept feasibility trial of a new intervention designed to address prenatal depressive symptoms to encourage tobacco and cannabis cessation. We will examine the initial feasibility and acceptability of the intervention using standard measures in addition to measures suggested by the collaborative. We hypothesize that 1) the intervention will be feasible to participants and 2) the intervention will be acceptable to participants.

The primary outcomes of the trial are the feasibility and acceptability of the novel intervention and abstinence from tobacco and cannabis use. Feasibility and acceptability of the intervention will be assessed using attendance, completion of intervention-related procedures, and the Acceptability of Intervention Measure (AIM). Abstinence will be measured by proportion of the participants who self-report no use of either substance and by calculating the proportion of participants with negative urine screens for THC and COT. Secondary outcomes include changes in depressive symptoms, tobacco, and cannabis use from the baseline assessment in pregnancy to 3 months postpartum.

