*** Identify the subgroups and provide a justification:**

We exclude individuals under age 18 from this work because the perinatal concerns and treatments for depression of individuals younger than age 18 are likely to differ from those of individuals 18 years of age or older and would require developmentally appropriate assessments and interventions.

8. Describe the power analysis used and cite your method of statistical analysis. If a power analysis is not possible, thoroughly justify the sample size required for the study, including appropriate literature citation (alternatively provide page reference in attached protocol):

Chi-square tests will be used to calculate differences in feasibility as a function of key intersecting identities (e.g., age, race, ethnicity, SM status) and use history variables. If feasibility is found to be significantly different by race or SM status, the analyses will be weighted to account for differences in attrition. We will assess the preliminary efficacy of the novel intervention to promote self-reported abstinence from tobacco and cannabis at the end of pregnancy (Time 3) and 12-16 weeks postpartum (Time 4). The proportion of self-reported abstinence among participants in the INT and EUC groups at Times 3 and 4 will be compared using chi-square tests of difference. We will stratify by race and sexual orientation to test for intersectional effects. Secondary analysis will examine differences in biochemically verified abstinence (urine dip test for presence of cotinine or THC) and depressive symptoms between INT and EUC using chi square tests and compare depressive symptoms (EPDS) scores in the two groups using two-sample t-tests. The Cochran Q test will be applied to self-reported tobacco and cannabis use across the 4 time points within the INT group to test whether there has been a change in the ratings over time. Next, a generalized linear mixed effects model (GLMM) with a logit link will be used to test the treatment effect (INT vs. EUC) and treatment by time interaction to test whether the rate of abstinence over time was steeper among the INT group compared to the EUC group. We have 70% power to detect a 15% difference in quit rates between INT and EUC, assuming a 25% intervention arm quit rate and 10% control arm quit rate.

Pregnant Women

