A trained research team member will contact potential participants by telephone and/or email. We will use the relevant telephone and email scripts to describe the study and gauge interest. A screening survey will be used to determine eligibility. The screening survey will be programmed on REDCap and made available through Pitt+Me, the recruitment flyer, lab websites, and as a link sent to individuals who contact research staff directly. Once screened eligible, interested individuals will be contacted by the research assistant who will review and obtain consent for participation. After obtaining consent, the research team member will schedule the participant for their first prenatal session. The participant will then be texted or emailed a link to their baseline assessment questionnaires on REDCap.

Baseline Assessment (T1):

Participants will complete the following questionnaires as part of the baseline assessment: Demographics, EPDS, Smoking and Alcohol Use Questionnaire, Cannabis Use Questionnaire, Perceived Stress Scale-4, Major Experiences of Discrimination. Participants will be paid \$30 using the Pitt Vincent payment system when questionnaires are completed. The baseline assessment is estimated to take 30-60 minutes.

Prenatal Sessions

Participants will meet virtually with a study interventionist over the course of 6 prenatal sessions. Sessions will include education and discussions on the topics and strategies listed below. The scheduling timeline of prenatal sessions will depend on the gestational age of the pregnancy at time of enrollment and so will be determined on a case-by-case basis. Sessions will last up to 30 minutes.

1: Self-monitoring targets/ problem identification. This may include recognition of depressive symptoms, urges for tobacco and cannabis, how one might be used to manage withdrawal from the other.

2: Psychoeducation. This may include the teaching of rationale for addressing psychological distress/mood, relationship of trauma to mood and behaviors, model of cessation and relapse prevention/ learn how cannabis may hinder tobacco cessation and increase depressive symptoms.

3: Behavioral Activation. This may include identifying reinforcing activities and activities incompatible with tobacco and cannabis use.

4: Cognitive restructuring. This may include understanding/addressing dysfunctional thoughts about mood/stress and dysfunctional thoughts about tobacco and cannabis use.

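### The only depressive-symptom outcome runs from pregnancy baseline to 3 months postpartum. The end-of-intervention EPDS is collected but used in no stated outcome or analysis, so prenatal change is not reported separately.

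*Protocol*

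**What the plan says.** Study Aims item 1 describes "a new intervention designed to address prenatal depressive symptoms to encourage tobacco and cannabis cessation". Research Activities item 1 places delivery before birth: "Participants will meet virtually with a study interventionist over the course of 6 prenatal sessions". No session after delivery is described. The T4 visit carries a urine-based incentive, but it concerns tobacco and cannabis, not mood.

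Study Aims item 1 and Study Design item 3 give the same single outcome for depressive symptoms: "Secondary outcomes include changes in depressive symptoms, tobacco, and cannabis use from the baseline assessment in pregnancy to 3 months postpartum".

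The EPDS is scheduled at all four assessments. At T1: "Participants will complete the following questionnaires as part of the baseline assessment: Demographics, EPDS". At T2: "Participants will complete the following questionnaires on REDCap as part of the end-of-intervention assessment: Demographics, EPDS". On the timing of T2: "This assessment will occur when participants are 32-36 weeks gestation". T3 (1 month postpartum) and T4 (3 months postpartum) also list the EPDS.

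Study Design item 8 gives the analysis. Depressive symptoms are to be compared between INT and EUC by chi-square tests, and the plan is also to "compare depressive symptoms (EPDS) scores in the two groups using two-sample t-tests". Neither comparison has a time point. The one within-group test over the four assessments, Cochran's Q, is for self-reported tobacco and cannabis use. Study Design item 2 says that the trial has a single arm.

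**The concern.** The stated route of action is to relieve depressive symptoms during pregnancy and thereby support cessation. T2 is the only EPDS measurement after baseline and before birth, so it is the only scheduled point that can show how symptoms moved over the intervention period. The stated outcome passes over it to a point about three months after birth.

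Change from T1 to T4 combines movement during the sessions with movement around delivery and in the newborn period. Two quite different courses can give the same T1-T4 difference: a fall by late pregnancy followed by a postpartum rise, or little movement in pregnancy followed by little movement afterwards. The outcome as defined cannot tell them apart, and no other planned EPDS analysis can be carried out. The trial could therefore report its secondary outcome in full without stating what happened to the symptoms that the sessions address.

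**Working it through.** No figure in the protocol needs to be reproduced here. The check has three parts.

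**1. Which EPDS measurements are used**

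| Assessment | EPDS collected (Research Activities item 1) | Used in stated outcome | Used in an analysis that one arm can run (Study Design item 8) |
|---|---|---|---|
| T1, baseline | yes | yes, start of interval | no |
| T2, 32-36 weeks | yes | not named | no |
| T3, 1 month postpartum | yes | not named | no |
| T4, 3 months postpartum | yes | yes, end of interval | no |

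The last column is empty because both EPDS analyses are INT versus EUC and Cochran's Q does not include the EPDS.

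**2. How much of the outcome interval lies after the end-of-intervention visit**

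Inputs: enrolment before 26 weeks (inclusion criterion 1); T2 at 32-36 weeks; T4 at 12-16 weeks postpartum (Study Design item 8). Assumptions: delivery at 40 weeks, and enrolment at 25 weeks (close to the latest allowed) or at 10 weeks (an early example).

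- T2 to T4 = (40 − week of T2) + weeks postpartum at T4. Shortest: (40 − 36) + 12 = 16 weeks. Longest: (40 − 32) + 16 = 24 weeks.
- T1 to T4 = (40 − week of enrolment) + weeks postpartum at T4.
  - Enrolment at 25 weeks: 15 + 12 = 27 to 15 + 16 = 31 weeks.
  - Enrolment at 10 weeks: 30 + 12 = 42 to 30 + 16 = 46 weeks.
- Share after T2 = (T2 to T4) / (T1 to T4).
  - Enrolment at 25 weeks: 16/27 = 59% to 24/31 = 77%.
  - Enrolment at 10 weeks: 16/42 = 38% to 24/46 = 52%.

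The share depends strongly on gestational age at enrolment. It is substantial in both cases.

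**3. What a paired T1-T2 estimate would offer**

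The half-width of a 95% confidence interval for a mean paired change, in units of the SD of the change, is t(0.975, n − 1)/√n. Enrolment is 25 (Study Design item 1). The lower completer numbers are assumed.

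| Completers | Half-width (SD of change) |
|---|---|
| 25 | 0.41 |
| 20 | 0.47 |
| 15 | 0.55 |

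The protocol gives no SD for EPDS change, so these cannot be turned into scale points. The precision suits estimation in a feasibility trial.

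**The case against.** The strongest reply is that the outcome sentence can be read as the span of follow-up rather than a two-point difference. It says that the outcomes include changes, in the plural. It also covers tobacco and cannabis use, which item 8 tests over all four assessments. That reading is possible. It does not close the gap, because item 8 extends the four-point analysis to substance use only and leaves the EPDS with comparisons against a group that does not exist.

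A second reply is that the choice of contrasts belongs in a statistical analysis plan, which may exist but is not shown. That holds for analytic detail. The outcome and its window, however, are fixed in this protocol, and item 8 does state an EPDS analysis, of the wrong kind. It is fair to add that part of the problem would disappear once item 8 is rewritten for one arm.

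Third, the postpartum window fits the protocol's own rationale: section B3 links prenatal symptoms to postpartum symptoms and relapse. This stands. A reader might infer that the T1-T4 outcome is mistaken or should rank below T1-T2. The documents do not support that, and the order of the two is a matter of preference.

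A reader might also infer that participants would be misclassified as benefiting or not benefiting. The protocol contains no responder rule, so nobody is scored in that way. Nor would the data be lost, since the T2 EPDS is collected in any case.

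Finally, T1-T2 change is itself confounded in a single arm, by regression to the mean and by the natural course of symptoms in pregnancy. Elevated symptoms are not an entry criterion either, so some participants may have little to reduce. This stands and limits what the added endpoint can claim.

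**Conclusion.** The point holds as a gap in the stated outcomes. The protocol names no outcome for depressive symptoms at the end of the prenatal intervention, collects the measurement that would supply one, and plans no EPDS analysis that a single arm can carry out. Under the assumptions above, between about two fifths and three quarters of the T1-T4 interval falls after T2. The conclusion does not depend on the exact share.

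It would go too far to say that a T1-T2 endpoint would show whether the intervention moved its target. It would remove delivery and the postpartum period from the interval, but it would not supply a control. Importance is moderate: both hypotheses concern feasibility and acceptability, depressive symptoms are a secondary outcome, and 25 participants are planned. The correction is still worth making because it is nearly free, and because naming the contrast in advance avoids choosing among the T2, T3 and T4 results after they are seen.

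**What to change.** - In Study Aims item 1 and Study Design item 3, add within-person EPDS change from T1 to T2 (32-36 weeks) as a named secondary endpoint. Keep change from T1 to T4 as a separate endpoint, labelled as postpartum.
- In Study Design item 8, replace the two-group EPDS comparisons with the mean paired change and its 95% confidence interval for each of the two intervals, with the number of pairs.
- State that the T1-T2 change is descriptive and cannot separate an intervention effect from regression to the mean or the natural course of symptoms.
- Identify each assessment by gestational or postpartum week as well as by label. Item 8 places Time 3 at the end of pregnancy, whereas Research Activities places T3 at 1 month postpartum.

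The cost is a change of wording, with no new visit, questionnaire or burden on participants. The downside is one more secondary estimate in a small sample, with the limited precision shown above.
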